5.10.3 SAFETY EVALUATION

The safety evaluation will be based on the reported complications and adverse events (AEs), including subsequent surgical interventions and neurological status. Complications/Aes shall be evaluated at each follow-up session, as well as throughout the study.

1. Complications/Adverse Events

All the reported complications/adverse events, whether device-related or not, including "anticipated" complications, will be recorded.

Refer to Section 5.14.4.1 for adverse event definitions.

2. Subsequent Surgical Intervention

Information regarding subsequent interventions will include category of procedure, as defined below, the reason for the procedure and whether or not the subsequent procedure constitutes a study failure.

Subsequent surgical intervention will be categorized as a revision, removal, reoperation, or supplemental fixation at the affected level/s, as defined hereinafter.

Revision – a second procedure that adjusts or in any way modifies or removes *part* of the original implant configuration, with or without replacement of a component. A revision may also include adjusting the position of the original configuration.

Removal - a procedure where *all* of the original system configuration are removed with or without replacement.

Reoperation – any surgical procedure at the involved level/s that is not removal, modification, or addition of any components to the system (e.g., irrigation and debridement).

Supplemental Fixation – a procedure in which additional instrumentation not under study in the Protocol is implanted.

Subsequent interventions in spinal studies include epidural injections, the implantation of spinal stimulators, and rhizotomies.

3. Neurological Status

A neurological examination will be performed preoperatively and at discharge, and at all postoperatively visits, to assess neurological status. The evaluation of neurological status will include motor, sensory, reflex, straight leg raising, and tenderness assessments, as hereby described. Each component shall be assessed separately on each anatomical side (left, right). The following paragraphs describe the five neurological examinations.

The **motor evaluation** measures the muscle strength in major muscle groups (Gluteus Maximus (hip extension); Iliopsoa (hip flexion); Quadriceps (knee extension); Hamstrings (knee flexion); Anterior Tibial Group (ankle dorsiflexion); Extensor Hallucis Longus (great toe extension); Posterior Tibial (ankle plantar flexion/eversion); and Flexor Halluces (great toe flection)). Muscle strength is evaluated on a 6-point scale ranging from 0 to 5 according to the following key

describing the ability of the patient to move the lower extremities against resistance provided by the examiner:

- ▶ 0 no movement;
- ▶ 1- muscle contraction;
- > 2 lateral movement;
- ➤ 3 against gravity;
- ➤ 4 against moderate resistance;
- \blacktriangleright 5 against full resistance.

Light-touch will test **sensation** for all lumbar and sacral dermatomes in comparison to the contralateral site. The sensation shall be graded as equivalent (normal), impaired, absent, as compared to the contralateral side.

Reflexes (Patella and Achilles) are evaluated according to Bate's Reflex Scale (a 5-point scale ranging from 0 to 4) as follows:

- > 0 − no reflex;
- > 1 somewhat diminished, low normal;
- \triangleright 2 average, normal reflex;
- > 3 brisker than average;
- ➤ 4 very brisk, hyperactive.

Straight leg raising is assessed by measurement of the degree of movement required to reproduce symptoms. A positive test is considered when the patient reports worsening of pain between 30 and 70 degrees of hip passive flexion while knee is extended.

Tenderness will be evaluated by palpation of the lower spine area – lumbar paraspinal region, lumber spinous process, sacroiliac joint, and sciatic notch. Tenderness shall be graded as negative or positive (*i.e.*, palpation provokes painful sensation).

 Patient Success –

Individual patient success with respect to *safety* is defined as:

- No worsening in neurological status (motor, sensory, reflex, straight leg raising, and tenderness assessments) and no new permanent neurological deficits present for at least 2 successive visits at or beyond 6 months (out to 24 months);
- Absence of device-related serious adverse events through 24 months;
- Absence of subsequent surgical interventions at the index level through 24 months.

5.11 EVALUATION OF SECONDARY OUTCOME MEASURES

A. Patient's Overall Well-Being and Satisfaction

Subject's overall well-being and satisfaction will be assessed using dedicated questionnaires.

SF-12 (Subject Overall Well-Being):

Subject's overall well-being (quality of life) will be assessed using the 12-Item Short Form Health Survey (SF-12), which is a multipurpose short-form quality of life instrument with 12 questions selected from the SF-36 Health Survey. SF-12 questionnaire is designed to measure general health status from the patient's point of view. Results are expressed in terms of two meta-scores: the Physical Component Summary (PCS) and the Mental Component Summary (MCS). The PCS Score is a composite of the Physical Functioning, Role Functioning, Bodily Pain and General Health Scales within the SF-12 instrument. The MCS is a composite of the Vitality, Social Functioning, Role-Emotional and Mental Health Scales within the SF-12 instrument. The SF-12 is a normative based instrument. PCS and MCS are computed using the rating on 12 questions from 0 to 100, where a 0 score indicates the lowest level of health and 100 indicates the highest level.

The SF-12 questionnaire will be administered preoperatively as well as at each postoperative visit, starting at 6 weeks visit.

VAS (Patient Satisfaction):

Patient satisfaction will be assessed using a 100 mm VAS, completed by the patient. Satisfaction scores shall be obtained from patient responses, and shall be expressed in millimeters (mm). The anchor points are "Completely Not Satisfied" (0 mm) and "Completely Satisfied" (100 mm). Patients shall be instructed to draw a single line across the scale at the point that best described their level of satisfaction.

VAS questionnaire for satisfaction will be administered at each postoperative visit, starting at 6 weeks visit.

B. Donor Site Pain

The assessment of pain at the donor site (iliac crest) shall be performed using scores determined from measurements of responses to pain question, provided on a 100 mm VAS. The anchor points are "No Pain" (0 mm) and "Severe Pain" (100 mm). Patients for which bone graft was harvested from their iliac bone will be instructed to draw a single line across the scale at the point that best described their level of pain at the donor site.

VAS questionnaire for donor site pain will be administered at each postoperative visit, starting at 6 weeks visit.

C. **Operative Information**

Parameters related to the surgery, such as blood loss and operation time will be also evaluated for all patients participating in the study.

The volume of *blood loss* during operation will be recorded for each patient, and average blood loss and standard deviation will be reported in cubic centimeter (cc). *Operation time* (skin-to-skin) will be recorded for each patient, and average operation time and standard deviation will be reported in minutes.

5.12 STUDY SUCCESS CRITERIA

The results of the study at 12 months and 24 months postoperatively for all participating subjects will be evaluated, with reference to the reported results from the

literature, as summarized in **Section 5.2.1**. In addition, assessment of success rate will be conducted at each time point, as applicable.

In addition to evaluating individual patient success as the primary composite endpoint, each element of the composite will be evaluated individually as secondary endpoints, as described below.

Fusion – Success for the fusion outcome measure will be defined as two year fusion rate comparable to the two and one year fusion rates presented in the literature. The pooled results of the Company literature research (for patients with DDD treated with pedicle screws with PLIF/ALIF/TLIF and/or PLF), as presented in **Section 5.2.1**, demonstrated at 12 and 24 months postoperatively fusion rates in the different studies ranging from 77% to 97%.

As discussed in **Section 5.2.1.A**, the weighted average for the fusion rate of the ten articles is 87.79%. Based on the literature, we believe our fusion rate will be 88%.

The assumed fusion rate of 88% has a 95% confidence interval of $\pm 6.4\%$ for 100 patients. Notably, the lower bound of this confidence interval, 81.6%, is within the range of the fusion rates reported in the selected literature.

Safety – Success with regard to safety outcome measure is defined as no worsening in neurological status (motor, sensory, reflex, straight leg raising, and tenderness assessments) and no new permanent neurological deficits (present for at least 2 successive visits at or beyond 6 months), absence of device-related serious adverse events, and absence subsequent surgical interventions at the index level, through 24 months, comparable to neurological deficit, device-related serious adverse events, and subsequent surgical interventions rates presented in the literature.

Based on the literature review in FDA's Executive Summary, the rate of these events in the literature control is 13.5%.

Therefore, the Company estimates that the adverse event rate for these events will be 13.5%. With a sample size of 100 patients, this adverse event rate has a 95% confidence interval of $\pm 6.7\%$.

As indicated above, it is believed that at the time all subjects from the IDE study complete one year follow-up, supporting safety data for 24 months will be available for about 45 patients from the ongoing, OUS study.

**Pain - Individual patient, clinically meaningful, improvement with respect to pain is defined as postoperative improvement at 24 months of at least 20 mm on a 100 mm VAS from the baseline level.**

Value of 73% of patients with \geq 20 mm improvement. This value is selected as it is consistent with the performance of the Silhouette Spinal Fixation System reported in P070031.

Function - Individual patient, clinically meaningful, improvement with respect to function is defined as postoperative improvement at 24 months of at least 15 points on the ODI graded on a 100-point scale as compared to baseline assessment.

Value of 55% of patients with \geq 15 points improvement. This value is selected as it is consistent with the performance of the control group reported in P050010.

Individual Patient Success (Overall Success)

Individual patient success (*i.e.*, overall success) will be determined at 24 months and is defined as a composite primary endpoint. An individual subject will considered a success if all of the following criteria are met:

- Presence of continuous bridging bone between the involved motion segment at 24 months, *i.e.*:
 - Presence of interbody bridging bone and absence of radiolucency > 50%; OR
 - Presence of left posterolateral bridging bone; OR
 - Presence of left posterolateral bridging bone.
- No motion on flexion/extension films at 24 months (success is defined as angular motion < 3° and translational motion < 3 mm);

- Improvement of at least 20 mm on a 100 mm VAS from baseline level at 24 months;
- Improvement of at least 15 points on the ODI graded on a 100 point scale at 24 months as compared to baseline;
- ➢ No worsening in neurological status (motor, sensory, reflex, straight leg raising, and tenderness assessments) and no new permanent neurological

deficits present for at least 2 successive visits at or beyond 6 months (out to 24 months);

- > Absence of device-related serious adverse events through 24 months;
- Absence of subsequent surgical interventions at the index level through 24 months.

The study will be considered a success if the overall success rate for the CarboClear Device is 41%. This value is selected as it is consistent with the performance of the control groups reported in P050010 and P070031.

5.13 STATISTICAL ANALYSIS

5.13.1 SAMPLE SIZE JUSTIFICATION

Fifty five (55) patients will participate in the IDE study. However, the statistical analysis will be conducted for a total sample size of 100 patients as the Company is adding data from ongoing OUS sites to data collected according to this IDE. FDA confirmed that the proposed IDE sample size, in addition to the ongoing OUS data, would be sufficient. It is emphasized, that prospectively enrolled patients at OUS sites will participate in the study presented in this IDE (i.e., will be part of the 55 patients of the IDE study), and will follow the same protocol that representing homogenous cohort of DDD patients with up to Grade I spondylolisthesis and no greater than mild stenosis. Only currently enrolled patients in the ongoing OUS sites that are adequately per IDE protocol (about 45 patients) will be considered in the statistical analysis. Adequacy for OUS study patients being included in the statistical analysis will be based, mainly, on patient meeting the eligibility criteria (inclusion/exclusion) for the IDE study, *i.e.*, DDD patients, with up to Grade I spondylolisthesis and/or with up to mild stenosis (the ongoing OUS study was approved for more heterogenic population). Other parameters, as detailed below, are very similar when comparing the ongoing OUS study and the study suggested in this IDE: The same system and surgical technique are used in both studies. The IDE study includes the use of an interbody fusion device while the OUS study does not. Thus, the data from the OUS study may be regarded as worst case in terms of fusion rates as only posterolateral fusion was made and interbody fusion device was not used. Patient population is

CARBOCLEAR PEDICLE SCREW SYSTEM

considered similar in both studies (demographically, as well as indications wise, as non-DDD patients will not be included in the statistics for the IDE study). The endpoints for the IDE study are also evaluated in the ongoing OUS study, using the same assessment tools: fusion (radiographs), safety, pain (VAS), function (ODI), and patient well-being (SF-12). Follow-up time points are similar in the ongoing OUS study (4 weeks, 3 months, 6 months, 12 months and 24 months) and the suggested IDE study (6 weeks, 3 months, 6 months, 12 months, and 24 months, and then annually, until the last patient completed 2-year follow-up).

As it is estimated that data for about 45 patients will be available from the ongoing OUS study, the total sample size is effectively 100 patients.

It is noted, that the suggested investigation is a confirmatory study, aimed at supporting the safety and effectiveness of the CarboClear System. As indicated before, comprehensive pre-clinical testing was conducted for the system, with good results, substantially equivalent to the results of cleared predicate devices (metal, rigid, pedicle screw systems). In addition, interim results from the ongoing, OUS study with the CarboClear System support the safety and effectiveness of the system for DDD patients (as summarized in the Investigator Brochure, the OUS trial enrolls DDD patients, as well non-DDD patients/patient with DDD and other pathologies. The latter may be regarded as worst case with respect to pedicle screw instrumentation and fusion in comparison to DDD patients).

Based on the above, and taking into account the selection of narrow indication for the study that results in homogenous population, the number of 55 subjects for this confirmatory study is thought to be sufficient (with statistical analysis of 100 patients).

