Inclusion Criteria:	 Subject has degenerative disc disease (DDD) at one level, from L2 to S1 vertebrae, with up to Grade I spondylolisthesis. DDD is defined as back pain and/or radicular leg pain with degeneration of the disc confirmed by patient history, radiographic studies, and physical examination, with one or more of the following factors (as measured radiographically, either by CT, MRI or plain film, myelography, discography, etc.): > osteophyte formation of facet joints or vertebral endplates; > decreased disc height, on average by > 2 mm; > scarring/thickening of ligamentum flavum, annulus fibrosis, or facet joint capsule; > herniated nucleus pulposus; > facet joint degeneration/changes; > vacuum phenomenon. Subject is candidate for single level intervertebral fusion, with or without posterolateral fusion, with implantation of intervertebral body fusion device and supplemental fixation. Subject age is between 21 – 72 years, and subject is skeletally mature. Pre-operative low back and/or leg/s pain (debilitating pain that causes a significant disturbance of the routine daily physical activities) ≥ 40 mm on a 100 mm Visual Analogue Scale (VAS). Pre-operative Oswestry Disability Index (ODI) score ≥ 40 	

percentage-point, indicating at least moderate disability (interpreted as moderate/severe disability).

- 6. Low back and/or leg/s pain is unresponsive to prior non-surgical management for a minimum of six months. Non-operative treatment includes pain medication, physical therapy and/or injections.
- 7. Patient must understand and sign the informed consent.
- 8. Patient is willing and able to meet the proposed follow-up schedule including return to follow-up visits and complete necessary study paperwork.
- 9. Patient is willing and able to follow the postoperative management program.
- *Exclusion Criteria:* 1. Previous fusion or fusion attempts, including anterior fusion or posterolateral fusion, at the index level.
 - 2. Previous fusion or fusion attempts at the adjacent levels.
 - 3. Prior decompression procedures that include removal of soft and bone tissue at the index or adjacent levels.
 - 4. Patient is not skeletally mature.
 - 5. Degenerative spondylolisthesis greater than Grade I.
 - 6. Spinal instability at the index level with ≥ 3 mm translation and/or ≥ 5 degrees angulation. Determination of instability will be assessed using flexion/extension lateral view radiographs.
 - 7. Isthmic spondylolisthesis.

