- f. Providing a clear Instructions for Use document (IFU) and Surgical Technique. Among other things, these documents include description of the system and its components (including figures), indications for use and contraindications, possible adverse events, warnings and precautions, instructions regarding system preparation, surgical procedure description, information regarding the compatibility of the product with other devices, and information regarding product packaging and sterilization.
- g. Conducting additional validations and verifications, as applicable, such as sterilization validation.

The following paragraphs specifically address the risks indicated above, and the measures by which those potential risks are minimized.

A. Risks Associated with Undergoing Surgery

General operative-related complications (such as infection/sepsis, bleeding/vascular injury, respiratory and cardiac complications, anesthesia, wound complications and

pain, *etc.*, as listed above) are expected to be similar in nature and not in higher rates compared to those seen with other pedicle screw systems, as the surgical procedure is the same.

As the implantation procedure is similar to that used for other pedicle screw system implantation, using similar surgical instruments, and as cleared interbody fusion device is used, no additional/special hazards are expected to rise from the operation procedure itself.

It is noted, that the implantation procedure and the performance of the surgical instruments were also evaluated during cadaveric study.

In addition, the CarboClear System is currently under multi-center study conducted out-of-the-US. So far, 47 patients were already treated with the system, with a follow-up duration of up to over one year (40 of which had diagnosis that complies with the indications proposed in the IDE (*i.e.*, DDD patients with up to Grade I spondylolisthesis). The following adverse event, which may be categorized as related to undergoing surgery, was reported in the said study:

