Regarding the risk of infection due to non-sterile device - the implants will be supplied sterile (by moist-heat steam) and labeled for single use. The multi-use surgical instruments will be supplied non-sterile, to be steam sterilized by the user. The steam sterilizations for the system components were validated to assure SAL of 10^{-6} , and bioburden tests are conducted periodically.

Information regarding the sterilization of the implants and the cleaning and sterilization of the reusable surgical instruments is provided in the Investigator Brochure.

Regarding the ongoing OUS study - it is emphasized, that no device-related adverse events or device malfunctions were reported in any of the 47 patients implanted with the system. No failure was observed to any of the components implanted (about 180 pedicle screws (and locking elements), with about 90 rods for all 47 patients operated).

In addition, as indicated earlier, fusion - determined by X-Ray images indicating continuous fusion in between transverse processes and/or facet joints (AP and lateral X-Rays) – was indicated in the following rates (for the 40 DDD patients; please note

that for part of the patients, evaluation of translational and angular motion using flexion/extension radiographs was also conducted):

- At 6 months (1 level): 25/26 patients (96.2%);
- At 12 months (1 level): 3/3 patients (100%);
- At 6 months (2 levels): 1/1 (100%).

The on-going clinical investigation with the CarboClear device also supports the proper visualization of implant components, either during operation or at follow-up period. Also, no allergic reaction to the implant was reported.

As it is postulated, based on all the above, that the risk of device breakage/loosening/disassembly/migration; non/delayed fusion; or foreign body reaction to the device, would not be at a higher rate than seen for other cleared, rigid, pedicle screw systems, it is expected that the risk of re-operation due to these risks will be at similar rate as the rate reported for other pedicle screw systems.

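### The rule that picks about 45 already-enrolled OUS-study patients for the 100-patient primary analysis is incomplete, and nothing requires it to be applied without sight of outcomes

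*Combined protocol and SAP*

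**What the plan says.** Section 5.13.1 states that "Fifty five (55) patients will participate in the IDE study", but that "the statistical analysis will be conducted for a total sample size of 100 patients". The remainder come from an ongoing OUS study. Only patients currently enrolled there are considered, and their number is put at about 45.

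On who qualifies, the section says: "Adequacy for OUS study patients being included in the statistical analysis will be based, mainly, on patient meeting the eligibility criteria". The sentence identifies these as the IDE study's inclusion and exclusion criteria. After an *i.e.* it restates them as DDD with no more than a Grade I slip and/or no more than mild stenosis, and it notes that "the ongoing OUS study was approved for more heterogenic population". No further ground is listed. The plan does not say who makes the selection, at what date, or what that person may see.

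The IDE patients are bound by all of 5.3 and 5.4: one level, a pain floor of 40 mm, "Pre-operative Oswestry Disability Index (ODI) score ≥ 40", an interbody device, and exclusions that include prior decompression, current smoking and morbid obesity.

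Section 5.14.2 gives interim OUS results. There were 47 patients treated, "40 of which had diagnosis that complies with the indications proposed in the IDE".

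Under 5.12 the study succeeds if the overall success rate is 41%. Section 5.2 calls the analysis descriptive.

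**The concern.** Nearly half of the primary analysis set is chosen after enrolment, from a study run under a different protocol, by a rule that can be read in two ways. On the wide reading every IDE criterion applies. On the narrow reading only diagnosis does, and patients outside 5.3 and 5.4 could be counted. The documents do not show which way that would push the composite. A patient with a low baseline score has less room to improve by 20 mm or 15 points, so such patients could lower the rate as well as raise it.

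The second issue is timing. Success rests on one observed proportion against a fixed 41%, with no control arm, test or confidence bound. If the membership of about 45 patients is still open when their outcomes are known, decisions about doubtful cases can be influenced by those outcomes, even unintentionally.

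**Working it through.** **1. The plan's own figures.** Section 5.12 gives 95% half-widths at n = 100, computed as 1.96 × √(p(1−p)/n).
- Fusion: 1.96 × √(0.88 × 0.12/100) = 6.4 points, as stated.
- Safety: 1.96 × √(0.135 × 0.865/100) = 6.7 points, as stated.

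Both depend on 55 + 45 = 100. No error rate or power is given for the 41% bar.

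**2. Can the rule be the full IDE criteria?** Inclusion 2 in 5.3 calls for an interbody device. Section 5.13.1 says the OUS study does not use one. At least that requirement must be waived, and the plan does not say whether others are.

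**3. What the interim count shows.** The 40 patients in 5.14.2 were counted by diagnosis. The fusion results reported for them include a two-level case (1/1 at 6 months), although inclusion 1 requires one level. The count of 40 also does not match about 45, and the difference is not explained.

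**4. What is visible, and when.** Section 5.14.2 already tabulates OUS fusion (one level: 25/26 at 6 months and 3/3 at 12 months) and reports no device-related adverse events in the 47. Section 5.7 expects two-year OUS data by the time all IDE patients reach 12 months. Section 5.12 says the same of 24-month safety data for about 45 OUS patients.

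**5. How many omissions cross the bar.** Read the rule as at least 41%. Start from 100 patients and leave out k OUS failures. The result passes if successes/(100 − k) ≥ 0.41.

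| Successes of 100 | k | Rate | Result |
|---|---|---|---|
| 40 | 0 | 40/100 = 40.0% | fail |
| 40 | 1 | 40/99 = 40.4% | fail |
| 40 | 2 | 40/98 = 40.8% | fail |
| 40 | 3 | 40/97 = 41.2% | pass |
| 39 | 0 | 39/100 = 39.0% | fail |
| 39 | 5 | 39/95 = 41.1% | pass |
| 38 | 7 | 38/93 = 40.9% | fail |

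For scale, 47 − 40 = 7 treated OUS patients fall outside the complying diagnosis.

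**6. A deliberate upper bound.** Assume 55 + 40 = 95 patients are fixed, all 7 others are discretionary, and only their successes are kept. With a ~ Bin(95, p) and b ~ Bin(7, p), the pass chance is P[(a + b)/(95 + b) ≥ 0.41]. Compare this with P(X ≥ 41) for X ~ Bin(100, p). The true rates p are assumptions; the documents give none.

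| True rate | Fixed set of 100 | Upper bound |
|---|---|---|
| 30% | 1.2% | 2.3% |
| 35% | 12.5% | 18.4% |
| 38% | 30.1% | 39.4% |
| 41% | 53.8% | 63.6% |

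**The case against.** The plan is less open than it first looks.

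- **The criteria are named.** A reader might infer that the pain and ODI floors, smoking and the rest are simply ignored for OUS patients. The documents do not support that: 5.13.1 cites the inclusion and exclusion criteria and asks for adequacy to the IDE protocol. The defect is ambiguity. The OUS details are in the Investigator Brochure, which is not among the documents, so the OUS study may have had similar floors.
- **The 40 are not declared to be the analysis set.** They appear in a risk summary. The two-level case shows how patients were counted there, not who will be pooled.
- **The outcomes shown are early ones.** A reader might infer that selection takes place with the deciding endpoint in view. No selection date is stated, and no 24-month composite is reported. Fusion in 29 of 30 readings (25/26, 3/3 and 1/1), with motion assessed in only part of the patients, gives little to select on.
- **The pool is limited.** It is confined to currently enrolled patients. The 7 were counted out on diagnosis and are not shown to be discretionary. On 47 treated and about 45 used, the slack is about 2.
- **Safeguards exist.** Section 5.13.2 compares IDE with OUS-study patients on pre-operative VAS, ODI, diagnosis and previous spinal surgery before combining. It allows pooling to be reconsidered, and it reports primary results by US and OUS sites.

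All of this limits the size of the problem, but the gap remains. The baseline comparisons come after selection and cannot detect selection on outcome, and 5.13.2 closes by treating pooling with the OUS study as already settled. Stratifying by site location does not isolate the selected patients: with at least 30 of 55 IDE patients in the US, up to 25 IDE patients fall in the same OUS stratum. The pooled 41% rule is unchanged in any case.

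**Conclusion.** The point stands as something that should be fixed. About 45% of the primary analysis set has no complete membership rule, and nothing requires the selection to be made without sight of outcomes, although 24-month OUS data are expected before IDE patients reach 24 months.

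The size is modest and illustrative. Three omitted failures rescue 40/100 and five rescue 39/100. One or two do nothing for 40/100, and seven do not rescue 38/100. A reader might infer that selection could turn a clearly poor result into a success; with the interim counts in the plan it could not. These figures assume that only failures are omitted, that the starting set is 100, and that the bar means at least 41%. The documents show no evidence that patients have been chosen by outcome.

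**What to change.** In 5.13.1, remove the word *mainly* and the restatement after *i.e.*, and state that:

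1. Every criterion in 5.3 and 5.4, except the interbody-device part of inclusion 2, is applied to every OUS patient enrolled at a named cut-off date.
2. It is applied from baseline and operative records only, by someone without access to post-operative data.
3. The list is locked before any 24-month OUS outcome is opened, and each patient left out is logged with the criterion failed.
4. Patients whose records cannot verify a criterion are flagged, and the composite is shown with and without them.
5. The composite is also reported for all OUS DDD patients and for the 55 IDE patients alone.

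The cost is one paragraph, a baseline chart check (47 patients at the interim count) and a few table rows. The downside is that fewer than 45 OUS patients may qualify. With 40, for example, n = 95 and the half-widths become 1.96 × √(0.88 × 0.12/95) = 6.5 points and 1.96 × √(0.135 × 0.865/95) = 6.9 points, against 6.4 and 6.7 now. The IDE-only analysis is wider: at n = 55 the same formula gives 8.6 and 9.0 points, so it serves as a check on the pooled result and not as a replacement.
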